Our target population includes subjects who are 50 years or older who are not receiving antihypertensive medications with MCI and AD. Our sample size is 72 for this trial. All 72 subjects will be invited to participate in the additional PET study.

SCHEDULE OF PROCEDURES FOR THE DURTAION OF THE STUDY

Phase:	SCREEN	BASELINE		TITRATION		FOL	LOW	-UP
Number of visits	1-2	1-3		2			4	
Months	-1	0		1-2	3	6	9	12
Informed Consent	Х							
Cognitive screening	Х							
Screening labs	X*							
Amyloid Positivity to assess eligibility	X**							
CSF for molecular analysis	X***	X***						Х
Weight/Height		Х		Х	Х	Х	Х	Х
Blood Pressure	Х	Х	NOI	Х	Х	Х	Х	Х
Safety labs			IZAT	X#	X#	Χ^	X#	Χ^
Brain MRI		Х	MO					Х
In-vivo A β and Tau PET scan	X**	X**	AND					Х
Vascular function measures		Х	R					Х
Cognitive Battery		Х				Х		Х
Functional battery (IADL, SPPB)		Х						Х
RAS biomarkers (blood and CSF)		Х				Х		Х
APOE genotype		Х						
Retinal scan and blood draw****								
Inflammatory/molecular biomarkers (proteomics /metabolomics)	X\$	X\$						X
Time (in minutes)	60-120	150-210		30	30	75	30	150-210

*: Screening labs include: CBC, CMP (BUN, CR, electrolytes, liver function), B12, TSH and PT/INR

**: Amyloid positivity can be assessed by either LP (CSF levels of amyloid) or PIB-PET. We will routinely use LP as the default method to determine Amyloid positivity however, in some instances e.g. a failed LP or delayed CSF results due to lab issues then we will use a screening PIB-PET instead. If a PIB-PET was done at screening, it WILL NOT be repeated at baseline. Subjects will only have Tau-Pet at baseline.

***: If subject has had an LP within the 6 months prior to their screening/baseline visit and samples are available for assessing eligibility and for measuring CSF outcomes then no LP will be done at screening. If CSF is only available for eligibility assessment (e.g. from PIB-PET/ clinical LP/assessment/ another research study and subject willing to share these samples) then an LP will be done to obtain CSF for the outcome measures (such as molecular analysis). This LP can be done at baseline instead of screening (since eligibility would have been already established).

****: Retinal scan +/- 10 cc blood draw are optional and can be done at any visit or after the completion of the study.

#: Safety labs at titration, 3 and 9 months include BMP (BUN, CR, electrolytes)

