6.12.2. ENROLLMENT, BASELINE, AND FOLLOW-UP

Once eligible, baseline evaluation will be completed. An LP will be done if not done during the screening visit. Once baseline data are collected, participants will be randomized into candesartan or placebo and seen every two weeks where study dose will be increased to 16 mg and 32 mg until MDT is achieved. They will be seen afterwards every three months until the study ends. All visits will have a +/- three week window except during medication escalation visits where the window will be +/- 5 days. An optional modified phone/virtual visit will be completed as needed for any visit to collect data that can be reasonably collected by phone. This change is in response to the COVID-19 stay home orders and in-person research activities will resume when normal business operations resume. Study procedures are shown in the **Table above**.

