7.4. FOLLOW-UP FOR ADVERSE EVENTS

All AE/SAE's will be recorded in the participant chart with start/stop date. The study physician may perform additional evaluations, visits, phone communication, repeat blood testing, or refer to the emergency room or the participant healthcare provider for medical care if necessary. If the event results in intervention discontinuation and/or study withdrawal, the participant will be followed for 2 months post-withdrawal with a monthly phone call. They will also be invited to perform the final visit evaluation including all study procedures planned for that visit if the participant has been in the study more than 5 month post baseline evaluation.

Follow-up on reported symptoms of hypotension or a BP<100/40 mm Hq: When a subject notifies the study team that they have either symptoms suggestive of hypotension (dizziness, weakness, near syncope, or syncope) or that their blood pressure is less than 100/40 mm Hg, the study physician will review the incident and determine if the subject is safe to continue in the study. The physician may discontinue the study medication immediately, elect to lower the dose of the study medication, ask subject to present to the study center for a safety evaluation, and/or monitor the subject blood pressure. The subject may continue in the study if blood pressure is >100/40 mm Hg on the lower dose of the study medication and had resolution of symptoms. In those on 16 mg and 32 mg, the doses will be decreased to the next lower dose. Those on 8 mg of candesartan, a trial of every other day 8 mg of candesartan will be attempted prior to discontinuation.

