8. INTERVENTION DISCONTINUATION

A subject may choose to withdraw from the study for any reason. The investigators may also request that the subject withdraw from the study, for safety or other reasons. The criteria for discontinuing a subject's participation include:

(1) the subject's request,

(2) adverse events that requires un-blinding or necessitate stopping the study drugs,

(3) persistent (>2 episodes on 2 separate days) of symptomatic hypotension or a blood pressure <100/40 mm Hg on 2 separate occasions despite adjusting study medication to the lowest dose (see section on follow-up on AE 7.4).(4) new clinically evident stroke or myocardial infarction or other event that limits ability to complete the study procedures

(4) inability to participate due to relocation or other personal reasons,

(5) renal failure (increase in serum Creatinine above 2.5 mg/dl) or hyperkalemia (greater than 5.9 meq)

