9. STATISTICAL CONSIDERATIONS

9.1. GENERAL DESIGN

The study is a 2-arm double-blinded RCT. The statistical analysis will follow the intention-to-treat approach. Intention-to-treat (ITT) and per-protocol analyses will be performed.

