11.4. PARTICIPANT COMPENSATION

Subjects will be compensated with gift cards for their effort and time at the following schedule:

- Screen Visit: \$25 + \$100 (for lumbar puncture procedure)
- Baseline Visits: \$100 (for visit + MRI) + \$75 for each PET scan (optional)
- Titration Visits (2): \$10
- 3 & 9 Month Follow Up Visits: \$25
- 6 Month Follow Up Visit: \$50 (cognitive testing, blood draw)

- 12 Month Follow Up Visits: \$100 (for visit + MRI) + \$75 for each PET scan (optional) + \$100 (for lumbar puncture procedure)
- Return Visit for blood redraw: \$20 and LP \$100 (as needed)
- Retinal Imaging: \$25Transportation: Up to \$30 for gas reimbursement and up to \$50 for taxi or shuttle service to the study site

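### As most naturally read, the plan collects no post-baseline CSF, vascular, imaging or cognitive outcome from participants who stop study drug for an adverse event by month 5, although the analysis is intention-to-treat

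*Combined protocol and SAP*

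**What the plan says.** Section 7.4 gives one rule for adverse events that lead to stopping the drug, leaving the study, or both: "the participant will be followed for 2 months post-withdrawal with a monthly phone call". An invitation to the final evaluation follows only "if the participant has been in the study more than 5 month post baseline evaluation". For hypotension, the same section describes staying in the study at a reduced dose: "The subject may continue in the study if blood pressure is >100/40 mm Hg on the lower dose of the study medication". Section 8 lists "adverse events that requires un-blinding or necessitate stopping the study drugs" among the criteria for ending a subject's participation.

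The schedule of procedures repeats the cognitive battery at months 6 and 12. CSF molecular analysis, brain MRI, PET and vascular measures are repeated at month 12 only. Section 6.12.2 adds "All visits will have a +/- three week window", with a tighter window for the dose-escalation visits.

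On analysis, section 9.1 says "The statistical analysis will follow the intention-to-treat approach" and also plans a per-protocol analysis. Section 9.3 compares change between arms with mixed models. Section 9 gives no missing-data assumption and no sensitivity analysis.

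**The concern.** An intention-to-treat comparison needs outcomes on everyone randomised, whether or not they are still on drug. Here a written rule, not chance dropout, ends outcome collection for people who stop early because of an adverse event.

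That reason may be related to treatment. Symptomatic or low blood pressure, creatinine above 2.5 mg/dl and potassium above 5.9 are stopping triggers in section 8, and section 7.1 names fainting, renal failure and hyperkalemia as possible candesartan complications. If more people stop early on candesartan, and they differ from those who continue, the arms are no longer comparable on the CSF, vascular, imaging and cognitive outcomes of Table 2. The same holds for the CSF amyloid and tau to which the précis ties target engagement. A month-12 value that was not collected cannot be recovered at the analysis stage.

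**Working it through.** **The plan's own figure.** The only size stated is 72 participants (précis), allocated 1:1 (section 5.1), so 36 per arm. It cannot be reproduced, because no alpha, power, effect size, SD or dropout rate accompanies it. The point does not depend on it.

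**Calendar check (no assumptions).** A month is 365.25/12 = 30.44 days and the window is 21 days.
- Earliest month-6 visit: 6 − 21/30.44 = 5.3 months.
- Earliest month-12 visit: 12 − 21/30.44 = 11.3 months.

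Both fall after the 5-month threshold, so no CSF, vascular, imaging or cognitive outcome is scheduled between baseline and month 5. Whether CSF is drawn at month 6 is unclear: the schedule lists RAS biomarkers in blood and CSF there, while section 11.4 pays for "cognitive testing, blood draw". Neither reading changes the result.

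**Illustrative bias, completer comparison.** Assumed: early loss p_C = 10% (candesartan) and p_P = 5% (placebo); stoppers differ from completers by d = 0.5 to 1.0 SD, alike in both arms; two-sided alpha 0.05.
- Analysable: 36 × 0.90 + 36 × 0.95 = 32.4 + 34.2 = 66.6, about 67 of 72.
- SE = √(1/32.4 + 1/34.2) = 0.245 SD.
- Bias = (p_C − p_P) × d = 0.05 × 0.5 = 0.025 SD, or 0.05 × 1.0 = 0.05 SD.
- Error = P(|Z + bias/SE| > 1.96). With bias/SE = 0.10 and 0.20 this is 5.1% and 5.5%.

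**Model that uses baseline.** Further assumed: baseline-outcome correlation 0.7, and half of d predicted by baseline.
- Bias halves to 0.0125-0.025 SD.
- SE = 0.245 × √(1 − 0.49) = 0.175.
- Error is 5.1-5.2%.

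**Range.** Loss of 25% v 5% with d = 1.0 gives a completer bias of 0.20 SD and error of 12%, or 0.10 SD and 8.5% with baseline. Bias is zero if stoppers do not differ, or if loss is equal and stoppers differ alike in both arms.

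**If half of the stoppers are retained (10% v 5% case).** With q = p/2 still missing, bias per arm = p·d − (p − q)·d/(1 − q).
- At d = 1.0: candesartan 0.10 − 0.05/0.95 = 0.0474; placebo 0.05 − 0.025/0.975 = 0.0244; difference 0.023 SD.
- At d = 0.5 the difference is 0.012 SD.
- Error is 5.0-5.1%, with 36 × 0.95 + 36 × 0.975 = 69.3 analysable.

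**Power cost of full retention.** Assumed: 10% of the candesartan arm stop and lose all effect, placebo loss is 5%, and the on-drug effect is δ. The diluted effect is 0.9δ, and the SE with all retained is √(2/36) = 0.236.
- δ = 0.66: completers 0.66/0.245 − 1.96 = 0.73, power 76.8%; all retained 0.594/0.236 − 1.96 = 0.56, power 71.2%.
- δ = 0.50: 53.2% for completers and 48.0% with all retained.

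The cost is therefore 5.6 and 5.2 points, even after counting the extra participants.

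**The case against.** - **The text is not unequivocal.** Section 7.4 joins stopping the drug and leaving the study with and/or, which implies that one can happen without the other. The phone calls are described as following withdrawal. Section 6.12.2 has randomised participants seen every three months to the end of the study, with no on-drug condition. Section 7.4 also does not say when the 5 months are judged, so someone who stops between months 3 and 5 could pass the threshold during the phone follow-up. This stands in part. A reader might infer that the plan definitely excludes every early stopper from later visits, but the documents do not go that far. What they lack is any off-drug visit schedule, and section 8 points towards ending participation.
- **The expected effect is small.** This stands. Section 2.2 reports small blood pressure declines without hypotensive symptoms in people with normal cognition, and the entry criteria, titration rule and dose step-down lower the risk further. Unequal loss is plausible, not shown.
- **Retention costs power.** This stands as a cost, about 5-6 points under the assumptions above. It is no reason to refuse, because intention-to-treat is the plan's own principle and the per-protocol analysis addresses the on-drug question.
- **Much of the primary objective is untouched.** Safety outcomes still count these participants, and the exploratory plot of dose against RAS activity would gain little from off-drug samples. Section 1 states the objective without the précis's reference to CSF amyloid and tau.
- **Removing the 5-month condition outright would add burden.** This stands. An early final evaluation with no minimum time could repeat LP, MRI and PET within weeks of baseline, so the fix keeps the condition for that case.
- **Other provisions might fill the gap.** They do not. The additional visits that section 7.4 allows are for adverse-event care, and the phone or virtual option in section 6.12.2 adapts a study visit without saying that people off drug still have one.

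**Conclusion.** The point holds in a limited form. As most naturally read, sections 7.4 and 8 leave participants who stop study drug for an adverse event by month 5 without any planned post-baseline CSF, vascular, imaging or cognitive outcome, which does not fit the intention-to-treat analysis of section 9.1. That conclusion rests on the wording and the calendar alone.

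The size of the consequence is not known. The mild case gives 0.025-0.05 SD and 5.1-5.5% error for completers, and less in a model using baseline. It rests on assumed loss rates, an assumed stopper difference and an assumed 5% test. A reader might infer serious error inflation from the 12% figure, but nothing in the documents supports the 25% v 5% loss and 1.0 SD difference behind it. Nor do they support a claim that the safety results are compromised.

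Severity is minor to moderate: the expected bias is small, but a stated rule discards data that the plan's own principle calls for, and the data cannot be collected later.

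**What to change.** - **Sections 7.4 and 8:** separate stopping study drug from withdrawing consent to follow-up. Invite everyone who stops drug and has not withdrawn consent to the scheduled month 6 and month 12 outcome visits, whatever the time of stopping, omitting any procedure the study physician judges unsafe or not feasible.
- **Early final evaluation:** keep the existing 5-month condition only here, for people who will not return at month 12. Analyse any such evaluation at its actual time.
- **Section 9:** add a sensitivity analysis that shifts missing candesartan outcomes over a range. It shows how far the result depends on them but does not replace them.

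The clinical criteria for stopping drug are unchanged.

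**Cost.** The change is to wording, with no new visit types or assays. Each person retained incurs the visit, scan, LP and assay costs already scheduled (not given in the documents), transport, and up to $400 in compensation under section 11.4: $50 at month 6, plus $100 + $100 for LP + 2 × $75 for PET = $350 at month 12. At the assumed 10% v 5%, that is 36 × (0.10 + 0.05) = 5.4 people and up to 5.4 × $400 = $2,160. People who are off drug for other reasons would add to this.

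Retention takes effort and some will decline LP or PET. The power loss from dilution shown above should be accepted openly.

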7.5. INCIDENTAL FINDINGS

Incidental findings (lab testing, neuroimaging or vascular testing) identified during the conduct of the study that do not require immediate medical care will be reported to the subject with instructions to seek medical care from the participant's healthcare provider. Those with incidental findings requiring urgent care will be referred to an emergency room in a facility of their choosing.

8. INTERVENTION DISCONTINUATION

A subject may choose to withdraw from the study for any reason. The investigators may also request that the subject withdraw from the study, for safety or other reasons. The criteria for discontinuing a subject's participation include:

(1) the subject's request,

(2) adverse events that requires un-blinding or necessitate stopping the study drugs,

(3) persistent (>2 episodes on 2 separate days) of symptomatic hypotension or a blood pressure <100/40 mm Hg on 2 separate occasions despite adjusting study medication to the lowest dose (see section on follow-up on AE 7.4).(4) new clinically evident stroke or myocardial infarction or other event that limits ability to complete the study procedures

(4) inability to participate due to relocation or other personal reasons,

(5) renal failure (increase in serum Creatinine above 2.5 mg/dl) or hyperkalemia (greater than 5.9 meq)

9. STATISTICAL CONSIDERATIONS

9.1. GENERAL DESIGN

The study is a 2-arm double-blinded RCT. The statistical analysis will follow the intention-to-treat approach. Intention-to-treat (ITT) and per-protocol analyses will be performed.

9.2. RANDOMIZATION

The study blinded biostatistician will provide oversight of randomization fidelity and blinding. Randomization will be stratified by use of cholinesterase inhibitors or Memantine (yes vs no) using a computerized random number generator (SAS, V9.4). Only the pharmacy will have access to the randomization lists. As the pharmacist is notified that an individual subject is eligible for randomization, the pharmacist prepares the appropriate blinded study product. The pharmacist will enter the subject ID, date of product randomization, and the unique allocation sequence number on a web-based data form.

9.3. DATA ANALYSIS

 Table 2 provides a list of main outcomes.

Table 2: Independent, main outcome and other variables to be used in the analyses		
Independent:	Group (Candesartan vs placebo)	
Safety outcome:	hypotensive episodes, symptoms (dizziness, weakness, cough) , creatinine >2.5 mg/dl , K>5.9 mEq/dl, number of discontinuations of candesartan, AE, SAE, Deaths	
CSF outcomes:	CSF tau, inflammatory proteins	
Vascular outcomes:	PWV, augmentation index	
Imaging outcomes:	Perfusion, hippocampal volume, vasoreactivity, Global SUVR (PiB and T807)	
Cognitive outcomes:	CDR, EXAMINER, HVLT, TMT (B and B-A)	

Baseline characteristics including demographic, APOe, social and cognitive measures will be compared between the 2 groups to assess randomization fidelity. The list of the main variables is shown in Table 3. We will compare the change in our outcomes over the study period between the treatment and placebo arms using Mixed Models. For the dose response analysis, the dose vs RAS activity will be plotted to explore the degree of modulation for each Ang peptide at the various doses.

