11.1. INSTITUTIONAL REVIEW BOARD (IRB) REVIEW	
11.2. CONSENTING PROCEDURE , INFORMED CONSENT FORMS, AND STUDY INFORMANTS	18
11.3. Participant Confidentiality	19
11.4. Participant Compensation	19
11.5. Study Discontinuation	20
12. PUBLICATION OF RESEARCH FINDINGS	20
13. REFERENCES	21

STUDY TEAM ROSTER

[name], MS (Principal Investigator)

Section of Geriatrics and Gerontology

[name], PhD (Co-investigator, Neurologist)

Department of Neurology

Department of Medicine

[name] (Co-investigator, MRI expert)

Division of Magnetic Resonance Research

Department of Radiology

[name] (Co-investigator, Neuropsychologist)

Department of Neurology

[name] (co-investigator, Medical Physicist) Department of Radiology

Department of Radiology

[name] (Co-investigator; Statistician)

Department of Biostatistics and Bioinformatics, Rollins School of Public Health, Emory University,

[name] (Co-investigator, Neuroproteomics)

Director, Emory NINDS-Neuroscience Proteomics Core Facility

PARTICIPATING STUDY SITES

Wesley Woods Health Center

Emory University Hospital Clinical Research Network

Executive Park Medical Campus

PRÉCIS

Study Title

Candesartan's Effects on Alzheimer's Disease And Related Biomarkers

Acronym

CEDAR

Objectives

Our *Primary objective* is to determine the safety and dose-response for target engagement of the treatment with escalating doses of candesartan in those with mild cognitive impairment (MCI) and Alzheimer's disease (AD) based on cerebrospinal fluid levels of amyloid and tau.

Our *secondary objectives* are to assess the efficacy of 1 year treatment of candesartan on biomarkers of vascular function, neurodegeneration, and neuro-inflammation; to assess the efficacy of 1 year treatment with candesartan on amyloid imaging; and to estimate the effect size of candesartan on cognitive and functional measures in MCI and AD.

Design and Outcomes

This is a double-blind placebo-control randomized clinical trial that compares candesartan to placebo in individuals with MCI who also have positive AD biomarkers. Our measures include cognitive function, cerebral perfusion and reserve, markers of vascular brain damage, atherosclerosis, arterial stiffness, vascular inflammation and endothelial function. Amyloid and Tau PET imaging will be collected on a subgroup of this trial.

Interventions and Duration

The intervention includes candesartan (8, 16, or 32 mg) or placebo. The duration of the study is 1 year.

Sample Size and Population

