4.2. EXCLUSION CRITERIA

(1) Intolerance to ARBs;

(2) Current use of ARBs or ACEI (use of antihypertensive medications other than ACEI or ARBs for other indications is allowed);

(3) Current diagnosis of hypertension or current use of antihypertensive medication that is prescribed specifically for hypertensive therapy;

(4) SBP less than 110 or DBP less than 40 mm Hg;

(5) Renal disease (Creatinine >2.0 mg/dl), hyperkalemia (K>5.5 meq/dl), platelets<50,000/μl, or INR>1.9;

(6) Active medical or psychiatric diseases that in the judgment of the investigator would affect the safety of the subject or scientific integrity of the study e.g. if the patient has hypothyroidism or low vitamin B12 that is contributing to the subject's cognitive impairment;

(7) Uncontrolled congestive heart failure reflected by poor exercise tolerance and shortness of breath;

(8) History of stroke in the past 3 years;

(9) Inability to have MRI (eg metal implants or cardiac pacemaker) with an exception for those who cannot have an MRI, if all other parts of the study are obtained successfully they may still be enrolled in the study, or cognitive assessment or inability to assess amyloid positivity (no LP and no amyloid scan);

(10) History of increased intracranial pressure (ICP) or bleeding diathesis (from disease states or from use of anticoagulants such as warfarin, heparin and related products, Rivaroxaban or Xarelto, Apixaban or Eliquis, Edoxaban or Savaysa, Dabigatraban or Pradaxa);

(11) Women of childbearing potential (non-menopausal);

(12) In those who are unable to demonstrate that they understood the details of the study (ie lack of decisionalcapacity to consent), a study partner/surrogate who can sign on their behalf will be required, otherwise they will be excluded;

(13) Current use of Lithium, as Candesartan may increase lithium concentration to toxic levels.

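### Table 2 lists kidney and potassium safety only as two rare threshold crossings; adding the creatinine and potassium values already being measured as continuous outcomes would be a cheap improvement

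*Combined protocol and SAP*

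**What the plan says.** The Précis states the primary objective as "to determine the safety and dose-response for target engagement of the treatment with escalating doses of candesartan", and section 1 repeats it in nearly the same terms.

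Table 2 in section 9.3 is captioned "Independent, main outcome and other variables to be used in the analyses". Its safety row has two laboratory items, "creatinine >2.5 mg/dl , K>5.9 mEq/dl", beside hypotensive episodes, symptoms, discontinuations, adverse events, serious adverse events and deaths. No creatinine or potassium value, or change in either, appears in any row. Section 9.3 then states: "We will compare the change in our outcomes over the study period between the treatment and placebo arms using Mixed Models".

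The same two cut-offs are a discontinuation criterion in section 8: "renal failure (increase in serum Creatinine above 2.5 mg/dl) or hyperkalemia (greater than 5.9 meq". Section 4.2 already excludes people at lower levels: "Renal disease (Creatinine >2.0 mg/dl), hyperkalemia (K>5.5 meq/dl".

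The footnotes to the Schedule of Procedures show that the values are collected. Before treatment: "Screening labs include: CBC, CMP (BUN, CR, electrolytes, liver function". On treatment: "Safety labs at titration, 3 and 9 months include BMP (BUN, CR, electrolytes", with the same panel plus a blood count at months 6 and 12. The schedule marks no safety labs at the baseline visit, so screening supplies the pre-treatment value.

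**The concern.** Entry limits keep out people near the two cut-offs, so few crossings should be expected in either arm. The laboratory part of the safety result could then be zero or near zero on both sides, and such a result cannot separate no effect from a moderate one. Meanwhile the database will hold repeated values that support an arm difference with an interval, in the mixed model the plan already intends to use. If those values are not named in advance, the choice of baseline, visits and handling of missing values is left until the data are in hand.

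**Working it through.** **Inputs from the plan.** 72 participants (Précis) at 1:1 (section 5.1) gives 36 per arm. The cut-offs are creatinine >2.5 mg/dl and K >5.9 (Table 2). The plan gives no power calculation, alpha, event rate or SD for these outcomes, so there is no stated figure to reproduce.

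**Assumptions.** Two-sided alpha 0.05. All rates, means, SDs, shifts and correlations below are assumed, with ranges. Potassium is in the units of the plan's cut-off.

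**1. What the threshold counts can show**

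- Exact two-sided 95% upper limit for 0/36: 1 − 0.025^(1/36) = 9.7%.
- Fisher p for k v 0 is 2·C(36,k)/C(72,k). For k = 5: 2 × 376,992/13,991,544 = 0.054. For k = 6: 2 × 1,947,792/156,238,908 = 0.025. So 6 v 0 is needed for p<0.05.
- Exact Fisher power at 36 per arm:

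| Assumed rates | Power |
|---|---|
| 5% v 1% | 0.6% |
| 10% v 1% | 11% |
| 15% v 1% | 36% |
| 20% v 1% | 65% |
| 24% v 1% | 81% |

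**2. What the continuous values can show**

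The 95% half-width at one visit, unadjusted, is t(0.975, 70) × SD × √(2/36) = 1.994 × SD × 0.2357.

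| Variable | Assumed SD | Half-width |
|---|---|---|
| Potassium | 0.3 | 0.14 |
| Potassium | 0.4 | 0.19 |
| Potassium | 0.5 | 0.24 |
| Creatinine, mg/dl | 0.2 | 0.09 |
| Creatinine, mg/dl | 0.3 | 0.14 |

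Adjusting for the screening value multiplies the half-width by √(1 − r²). For potassium at SD 0.4, r = 0.5 gives 0.188 × 0.866 = 0.163, and r = 0.7 gives 0.188 × 0.714 = 0.134. With 20% missing (29 per arm), the unadjusted figure is 2.003 × 0.4 × √(2/29) = 0.21.

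**3. Power for assumed shifts (two-sample t test, one visit)**

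- Potassium, shift 0.3: 88% at SD 0.4 (99% at SD 0.3, 71% at SD 0.5). At SD 0.4, adjusted at r = 0.5, it is 95%. With 29 per arm it is 80% unadjusted.
- Potassium, shift 0.2: 55% at SD 0.4 (80% to 39% over SD 0.3 to 0.5).
- Creatinine, shift 0.1 mg/dl: 55% at SD 0.2 and 29% at SD 0.3. Adjusted at r = 0.7, these become 83% and 50%.

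**4. The same potassium shift on both scales**

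Take normal values with mean 4.3 and SD 0.4, and a shift of 0.3. The chance of K >5.9 at one visit is P(Z > 1.6/0.4 = 4.0) = 0.003% without the shift and P(Z > 1.3/0.4 = 3.25) = 0.06% with it. Over six on-treatment panels (two titration, four follow-up), the shifted figure is at most 6 × 0.058% = 0.35%. The threshold outcome would almost surely read zero in both arms, while the continuous comparison of the same shift has the 88% power in step 3.

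**5. Dilution**

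If 20% of the candesartan arm return to no shift after dose reduction or stopping, the month 12 difference becomes 0.3 × 0.8 = 0.24. One-visit power at SD 0.4 then falls from 88% to 71%.

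**The case against.** Absence from Table 2 is weak evidence that a variable will go unanalysed. The lead-in presents the table as covering the main outcomes. Section 9.3 itself plans a dose plot of angiotensin peptides, which the table omits; CSF amyloid, named in the Précis objective, is missing too, as are IADL and SPPB. Section 9.3 also cites a Table 3 that is not in the text available. A reader might infer that the plan leaves creatinine and potassium values unanalysed or unreported. The documents do not support that; they show only that the values are not named in the outcome list.

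The two cut-offs match the plan's own definitions of renal failure and hyperkalemia in sections 7.1 and 8, so listing them as safety events is coherent. The plan states no test or power target for safety, and low power for rare events comes with any trial of 72. Adverse events and discontinuations could also catch some kidney or potassium problems. All of this stands, but those too are sparse counts and would not show a shift below the cut-offs.

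Finally, a mean shift is not the risk of a harmful value, and every power figure for the continuous outcomes rests on assumptions. This also stands. It limits the claimed gain to an interval for the mean shift and is why a descriptive count of high values should sit beside it.

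**Conclusion.** The point holds as a cheap improvement. Table 2 names only the dichotomised form of two measurements that the trial already takes repeatedly, and at 36 per arm that form carries little information on the arm difference. This part needs no assumed SD, and exact power stays at or below 36% for rates up to 15% v 1%. The gain from the continuous form is an interval with a half-width of 0.14 to 0.24 for potassium and 0.09 to 0.14 mg/dl for creatinine, at the assumed SDs.

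Two stronger conclusions are tempting and should not be drawn. One is that the continuous analysis secures adequate power: that depends on the assumed shift, and for creatinine power may be no better than 29% to 55% unadjusted. The other is that a null mean difference would establish kidney and potassium safety: a mean can hide a few high values, and later means can be diluted. Nor is any cut-off shown to be wrong. Blood pressure is outside this point, since Table 2 lists hypotensive episodes, dizziness and weakness. If Table 3 exists and lists the laboratory values, the point reduces to a wrong cross-reference.

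**What to change.** Keep every event now in Table 2 and add one line: *serum creatinine and potassium at all scheduled visits: arm difference in change from the screening value with 95% CI, by visit, from the planned mixed model, using all available values under ITT.* State whether the model adjusts for the screening value; the narrower intervals above assume that it does. Show titration and month 3 as well as month 12, because the early differences are less exposed to dilution.

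As description only, report the number per arm with any post-baseline value above the entry limits in section 4.2 (creatinine >2.0, K >5.5). These are reporting levels, and no clinical threshold changes.

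If Table 3 already lists these values, correct the cross-reference instead.

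The cost is wording in Table 2 and section 9.3 and a small analysis, with no extra blood draw. The downsides are a few more safety estimates, to be reported as estimates, and later means that may be diluted by dose reduction (section 7.4), discontinuation (section 8) and phone visits, at which blood may not be drawn (section 6.12.2).
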